## Appendix 7 Expanded List of Allowed Concomitant Medications

- Prophylactic therapy for steroid-induced bone loss (calcium with Vitamin D and/or a bisphosphonate).
- Low dose aspirin is allowed for cardiovascular prophylaxis.
- Minor GI AEs (such as nausea, vomiting and diarrhea) may be treated symptomatically (e.g., with loperamide for diarrhea or standard anti-emetics such as metoclopramide or domperidone for nausea and vomiting). Proton pump inhibitors or ranitidine are permitted for dyspepsia or gastric protection. Magnesium or aluminum containing antacids may be used, but should not be taken at the same time as study treatment; such antacids, if required, should be taken either 1 hour before or 2 hours after study treatment.
- Amphotericin or oral nystatin are permitted as infective prophylaxis against fungal infections, and low-dose sulfamethoxazole/trimethoprim is permitted as prophylaxis against *Pneumocystis carinii pneumonia*.
- Granulocyte colony stimulating factor is allowed to manage neutropenia in the presence of major infection (i.e., infections requiring IV antibiotics).
- Oral or IV iron preparations for iron deficiency and/or anemia.
- Erythropoietin is permitted for treatment of severe anemia (hemoglobin <10 mg/dL).
- Cytomegalovirus prophylaxis is permitted for example with oral valganciclovir.
- Acute intermittent administration of NSAIDs for not greater than 7 consecutive days is permitted.
- Lipid-lowering therapies (e.g., statins) will be used as clinically indicated.
- Antimalarials should be prescribed when clinically indicated.
- Angiotensin-converting enzyme inhibitors, ARBs, and aliskerin and other therapies are recommended, as per standard guidelines but if used their dose must be stable throughout the study. In addition subjects must be on a stable dose of ACE inhibitors or ARBs for 4 weeks prior to enrollment.
- In the case of uncontrolled hypertension (systolic BP >165 mmHg or diastolic >105 mmHg on 2 successive measurements), the addition of a diuretic or calcium channel blocker only are permitted, together with dose decreases or

interruption of study treatment per the instructions in Section 7.9, [Increased Blood Pressure](#).

[figure not shown]

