### 7.8.2 Allowed Concomitant Medications

These medications are permitted during the study:

- Topical steroids (e.g., nose, scalp, skin, inhaled)
- Antimalarials should be prescribed when clinically indicated
- Herbal supplements can be used with caution and depending on active ingredients

Treatments which may be used as medically indicated, according to the judgment of the Investigator can be found in [Appendix 7](#). Treatments not included in this list may be acceptable in the study; such treatments should be verified with the Medical Monitor prior to use. A summary of treatment and food restrictions can be found in [Appendix 8](#).

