## Appendix 8 Summary of Treatment and Food Restrictions

[figure not shown]
Treatment	Washout Period	During Treatment	Reason
Immunosuppressants other than those allowed by protocol	30 days	Prohibited	Interferes with study efficacy endpoints
Aminoglycosides Amphotericin B Melphalan Ketoconazole Rifampin	14 days	Prohibited	May potentiate toxicity
NSAIDs chronic dosing (>7 consecutive days)	Prohibited	Prohibited	May potentiate nephrotoxicity
P-gp substrates	To be monitored	To be monitored	Drug-drug interaction
P-gp inhibitors	To be discussed with Medical Monitor	To be discussed with Medical Monitor	Drug-drug interaction
Androgenic steroids Cimetidine Fluconazole, itraconazole Macrolide antibiotics (azithromycin, clarithromycin, erythromycin) Metoclopramide Barbiturates and derivatives Carbamazepine Octreotide acetate Phenytoin Sulfadimidine (intravenous) Theophylline	To be discussed with Medical Monitor	To be discussed with Medical Monitor	Drugs interfering with Orelvo metabolism
ACE inhibitors and ARBs	No change or introduction during screening	Change or commencement prohibited	Interfere with primary endpoint assessment
Foods Grapefruit and grapefruit juice	24 hours	Prohibited	May affect the metabolism of Orelvo

[figure not shown]
Abbreviations: ACE = Angiotensin converting enzyme; ARB = Angiotensin receptor blocker; NSAID = Non-steroidal anti-inflammatory drug; P-gp = P-glycoprotein.

[figure not shown]

[figure not shown]

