#### **6.1.3 Per-Protocol Population**

The Per-Protocol (PP) population will be a subset of the ITT consisting of those subjects who:

- Satisfy all of the inclusion / exclusion criteria
- Do not have any treatment administration errors
- Do not take prohibited concomitant medications

All protocol deviations will be assessed and documented on a case-by-case basis before the database lock and in a blinded fashion. Deviations considered to have a serious impact (major protocol violation) on the efficacy results will lead to the relevant subject being excluded from the PP population. Before database lock, potential subject exclusions from PP population will be reviewed by the Sponsor and documented in a subject evaluability document (██████████).

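### Protocol Appendices 7 and 8 give amphotericin opposite statuses, and metoclopramide different conditions, with no rule on which appendix prevails

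*Protocol*

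**What the plan says.** Protocol Section 7.8.2 sets up Appendix 7 as the list a site may act on: "Treatments which may be used as medically indicated, according to the judgment of the Investigator can be found in" Appendix 7. For drugs off the list it adds: "Treatments not included in this list may be acceptable in the study; such treatments should be verified with the Medical Monitor prior to use". The section closes by also pointing the reader to Appendix 8.

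Appendix 7 says "Amphotericin or oral nystatin are permitted as infective prophylaxis against fungal infections". For minor gastrointestinal events it allows "standard anti-emetics such as metoclopramide or domperidone for nausea and vomiting". Neither entry carries a Medical Monitor condition.

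Appendix 8 has a row listing "Aminoglycosides Amphotericin B Melphalan Ketoconazole Rifampin". The row gives a 14-day washout, a prohibition during treatment, and toxicity as the reason. A separate row, which includes "Metoclopramide Barbiturates and derivatives Carbamazepine", requires discussion with the Medical Monitor both for washout and during treatment, because the drugs in it interfere with the metabolism of the study drug.

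On the analysis side, SAP Section 6.1.3 lists as one condition for the Per-Protocol population that subjects "Do not take prohibited concomitant medications".

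**The concern.** A site reads Section 7.8.2, finds amphotericin in Appendix 7 and concludes that it may be used for antifungal prophylaxis. A site that starts from Appendix 8 finds amphotericin B prohibited. Both have followed the protocol as written. The first may have given a drug that the protocol bars elsewhere for toxicity, in a trial where renal function is a managed risk of the study drug (Protocol Section 2.1) and eGFR is part of the primary endpoint.

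The same conflict reaches the analysis through the Per-Protocol population. Whether an amphotericin user took a prohibited medication depends on which appendix the person classifying deviations happens to open.

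For metoclopramide the stake is smaller. Two sites could differ on whether the Medical Monitor must be consulted first, although the drug is barred in neither place.

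**Working it through.** No arithmetic applies. The check is a side-by-side reading of Protocol Sections 7.8.1 and 7.8.2, Appendices 7 and 8, and SAP Section 6.1.3.

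| Drug | Section 7.8.2 with Appendix 7 | Appendix 8 | Relation |
|---|---|---|---|
| Amphotericin / amphotericin B | Permitted as antifungal prophylaxis; no route, formulation or consultation condition | 14-day washout; prohibited during treatment; reason is toxicity | Direct conflict |
| Metoclopramide | Allowed as a standard anti-emetic, at Investigator judgment | Medical Monitor discussion for washout and during treatment; reason is study-drug metabolism | Different condition, not a prohibition |

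**1. Does the main text settle it?** No. Section 7.8.1 names ketoconazole and rifampin, which share the Appendix 8 row with amphotericin B, but names neither amphotericin nor metoclopramide. It introduces Appendix 8 as further restrictions. Section 7.8.2 cites both appendices. Neither section ranks them.

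**2. Can route or formulation separate the amphotericin entries?** Not on the text. In Appendix 7 the word for oral use is attached to nystatin only. Elsewhere the authors state a route when they mean one: Appendix 7 specifies it for valganciclovir and iron, and Appendix 8 marks sulfadimidine as intravenous. They also write matching carve-outs when a drug is allowed in one circumstance and barred in another. Appendix 7 permits NSAIDs for up to 7 consecutive days, and Appendix 8 bars them beyond 7. Amphotericin has no such pairing.

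**3. Do the metoclopramide entries differ in practice?** Yes, mildly. Section 7.8.2 reserves Medical Monitor verification for treatments not on the Appendix 7 list. Metoclopramide is on it, so a site working from that section and that appendix gets no prompt to call. Appendix 8 gives one.

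**4. What reaches the analysis?** The per-protocol criterion concerns prohibited medication. Amphotericin is prohibited under one appendix and permitted under the other, so the criterion has two answers. Metoclopramide is prohibited in neither, so these appendices do not bring it under the criterion. The per-protocol analysis is a supplementary analysis of the primary endpoint (SAP Section 6.11.2.3). The Clinical Endpoints Committee also receives prohibited-medication data (SAP Section 6.11.2.1), but the response definition disqualifies on rescue medication for lupus nephritis, not on prohibited medication as such.

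**The case against.** The best case for the protocol has three parts.

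*Different forms may be meant.* Appendix 7 limits its permission to prophylaxis and pairs amphotericin with an oral agent, and Appendix 8 uses a slightly different name. This may well be the intent. It cannot be established from the text, because no route is given for amphotericin in either place, so it is a reason to write the distinction down.

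*The appendices are cumulative.* Section 7.8.2 ends by sending the reader to Appendix 8, so an Appendix 7 drug may simply carry any extra condition stated there. For metoclopramide this is a reasonable reading, and it is why that part is the lesser one. It does not remove the difference, because the same section asks for verification only of unlisted treatments. For amphotericin a cumulative reading does not help: a permission plus a prohibition leaves nothing permitted.

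*There is a decision process.* A reader might infer that the per-protocol criterion cannot be applied at all. The documents do not support that. SAP Section 6.1.3 has deviations assessed individually, blinded and ahead of database lock, with exclusion for those judged to affect efficacy results seriously. Protocol Section 17.1 likewise provides for individual minor or major classification. A decision can be reached; what is missing is one rule behind it.

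A reader might also infer that every subject needing antifungal prophylaxis or an anti-emetic is affected. That goes too far: Appendix 7 names oral nystatin and domperidone in the same sentences, and Appendix 8 names neither.

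**Conclusion.** The point stands as an internal inconsistency. For amphotericin it is a direct clash between permission and prohibition with no precedence rule. For metoclopramide it is a smaller difference over who must be consulted.

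Its size cannot be computed. It touches only subjects actually given one of these drugs, and the documents contain no usage figures. The per-protocol consequence is limited to amphotericin.

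A reader might take this as a threat to the primary result. The documents do not support that. The ITT population is all randomized subjects, and the primary logistic model, the significance level and the sample size do not depend on either appendix. Nor should the Appendix 8 reason be read as kidney toxicity specifically: that wording appears in the NSAID row, while the amphotericin B row speaks of toxicity in general.

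The conclusion assumes that the two amphotericin names refer to the same drug unless the protocol says otherwise, and that the Appendix 8 rows read as they appear in the available text.

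**What to change.** Reconcile Section 7.8.2, Appendix 7 and Appendix 8 so that amphotericin and metoclopramide each have one status. If a distinction by route or formulation is intended, state it in both appendices, and confirm that the concomitant-medication record captures that detail; Section 7.8 mentions dosage, dates and reason for use, but not route. State which text governs if the appendices ever differ. Which status is right is a clinical decision for the sponsor and is not proposed here.

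Then name the reconciled list as the reference for the prohibited-medication criterion in SAP Section 6.1.3, before the blinded deviation review, and record in the subject evaluability document how any amphotericin use under the unreconciled text was classified.

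The cost is clarification wording in the protocol and one cross-reference in the SAP. No change to the primary model, error control or sample size follows.

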### 7.9 Increased Blood Pressure

For all subjects, the target systolic pressure is  $\leq 130$  mmHg and the target diastolic pressure is  $\leq 80$  mmHg. Investigators should use all means possible permitted in the protocol to maintain the BP within these limits. If no further adjustment of antihypertensive therapy is possible, the subject should be discussed with the Medical Monitor.

If on any study day, systolic BP is  $>165$  mmHg or diastolic BP is  $>105$  mmHg and is associated with symptoms of hypertension (i.e., persistent headache, altered mental status, shortness of breath, chest pain consistent with angina pectoris, symptoms of heart failure, evidence of renal insufficiency of new onset, evidence of hypertensive retinal injury [hemorrhages, papilledema]), study treatment should be held, the Medical Monitor contacted, and the subject treated as per Investigator local practices and best judgment. The subject will continue with all study visits per the [Schedule of Events](#). Study treatment must not be reintroduced without prior discussion with the Medical Monitor.

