#### **9.1.3.1 Blood Pressure Management**

Blood pressure and HR will be measured with the subject in a sitting position after 5 minutes of rest. The procedure for standardized measurement of BP is detailed in [Appendix 2](#).

If the BP measure is confirmed to be >130/80 mmHg (i.e., by the mean of the second and third repeats of 3 readings), the subject's BP will be managed per local practice. If the BP remains uncontrolled with the maximal doses of first and second-line antihypertensive therapies referenced in [Appendix 1](#), then the Investigator should contact the Medical Monitor to consider dose adjustment of the study treatment. See Section 7.9, [Increased Blood Pressure](#) for management of increased BP.

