## **Appendix 1 Drug Therapy for the Treatment of Hypertension**

Antihypertensive drug therapy for subjects who either have hypertension at screening or who develop hypertension while on study treatment may include the following:

- Dihydropyridine calcium channel blockers (e.g., amlodipine, nifedipine)
- Alpha-1-adrenergic blocking agents (e.g., doxazosin)
- Alpha-beta-blockers (e.g., carvedilol, labetalol)
- Thiazide diuretics (e.g., chlorthalidone or hydrochlorothiazide)

Excluded Drugs: While the ARBs and ACE inhibitors may also be effective in calcineurin inhibitor-associated hypertension, their dose adjustment or commencement is not permitted in this trial (see Section 7.8.1, [Prohibited Medications](#)).

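### Appendix 1 gives amlodipine a goal 10/10 mmHg looser than the protocol's 130/80 limit, and Appendix 7 does not allow Appendix 1's only second-line drug to be newly added above 165 or 105 mmHg

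*Protocol*

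**What the plan says.** **Target.** Protocol Section 7.9 opens with "For all subjects, the target systolic pressure is" at most 130 mmHg, with diastolic at most 80 mmHg, and expects investigators to use every permitted means to stay there. Section 9.1.3.1 acts on the same limit: "If the BP measure is confirmed to be >130/80 mmHg", the subject is managed by local practice. Section 9.2.5 requests an unscheduled visit for confirmed readings above it. In the recommended therapies of Appendix 1, the amlodipine line starts at 5 mg daily with a goal below 140/90 mmHg and moves to 10 mg if the result is not satisfactory within two weeks. No other drug line there carries a pressure goal.

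**Drugs that may be added.** Appendix 1 covers subjects with hypertension at screening or "who develop hypertension while on study treatment may include the following", and lists four classes. One of them is "Alpha-beta-blockers (e.g., carvedilol, labetalol"). The recommended sequence is one first-line agent (amlodipine, nifedipine XL, or a thiazide-type diuretic), then labetalol, the only second-line entry, after a partial response. Appendix 1 sets no upper pressure limit on that sequence. Section 9.1.3.1 builds on it: if pressure stays uncontrolled on maximal first- and second-line doses, "then the Investigator should contact the Medical Monitor to consider dose adjustment of the study treatment".

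For systolic above 165 or diastolic above 105 on two successive readings, Appendix 7 says "the addition of a diuretic or calcium channel blocker only are permitted, together with dose decreases" or interruption of study treatment as described in Section 7.9. For a subject above the same levels whose reading "and is associated with symptoms of hypertension", Section 7.9 holds study treatment, calls for contact with the Medical Monitor, and has "the subject treated as per Investigator local practices and best judgment". It names no drug class.

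**The concern.** These are operative safety instructions that give different answers to the same clinical question. A site that works from the amlodipine line can regard 136/86 as success and stay at 5 mg, although three body sections treat that reading as too high. If it stops there it also does not reach the maximal doses at which Section 9.1.3.1 asks for Medical Monitor contact. A site that follows the Appendix 1 sequence and adds labetalol at, say, 170/108 acts as one appendix recommends and outside what another permits. The protocol gives no reason why labetalol should be acceptable at lower pressures and not at these.

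Blood pressure matters for this drug. Section 2.1 singles it out, with renal function, for dose management. Section 1.2.5 reports more hypertension adverse events on voclosporin than on placebo in Phase 2, although mean pressure fell in all groups. Changes to ACE inhibitors and ARBs are already barred, so the choice of drugs is narrow before Appendix 7 narrows it further.

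A secondary matter is deviation status. Section 17.1 allows no waivers, and SAP Section 6.1.3 bases the per-protocol population partly on prohibited medication. Whether labetalol added in this range counts as a violation would fall to the blinded case-by-case review.

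**Working it through.** The plan gives no calculated figure on this point, so the check sets the texts side by side.

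**Target**

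| Place | Limit or goal (mmHg) |
|---|---|
| Section 7.9, all subjects | at most 130 and at most 80 |
| Section 9.1.3.1, action when confirmed | above 130/80 |
| Section 9.2.5, unscheduled visit when confirmed | above 130 or above 80 |
| Appendix 1, amlodipine line | below 140/90 |

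- Difference: 140 − 130 = 10 systolic; 90 − 80 = 10 diastolic.
- The two goals disagree when systolic is below 140 and diastolic is below 90, but systolic is above 130 or diastolic above 80.
- Example 136/86: 136 < 140 and 86 < 90, so the Appendix 1 goal is met. 136 − 130 = 6 and 86 − 80 = 6, so the Section 7.9 target is missed by 6 mmHg on each component.
- Reach: Appendix 1 has 3 first-line drug lines + 1 second-line = 4, and the conflicting goal stands on 1 of the 4.

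**Drugs that may be newly added above 165 or 105**

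| Appendix 1 class | Role in the recommended sequence | Addable under Appendix 7? |
|---|---|---|
| Dihydropyridine calcium channel blockers | first line (amlodipine, nifedipine XL) | yes |
| Thiazide diuretics | first line (chlorthalidone or hydrochlorothiazide) | yes |
| Alpha-1 blockers | listed, not in the sequence | no |
| Alpha-beta-blockers | second line (labetalol) | no |

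- Classes not addable: 4 − 2 = 2.
- Named second-line agents not addable: 1 of 1.
- First-line drug lines still addable: 3 of 3.

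**Who is left in the gap**

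1. Symptomatic subjects above 165 or 105: Section 7.9 leaves treatment to local practice. Appendix 7 makes no exception for symptoms, so the texts conflict, but the body section supplies a route.
2. Subjects already on labetalol when they cross the threshold: Appendix 7 restricts additions, so they may continue.
3. Asymptomatic subjects above 165 or 105 on two successive readings and not yet on labetalol: Appendix 1 recommends it after a partial response to first-line therapy, and Appendix 7 does not allow it to be added. This is the main residual gap.

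**The case against.** The strongest reply is that the body of the protocol already governs. Sections 7.9, 9.1.3.1 and 9.2.5 agree on 130/80, and a confirmed 136/86 prompts an unscheduled visit whatever the amlodipine line says. Appendix 1 is permissive, and its amlodipine line does not forbid 10 mg in pursuit of 130/80. Reaching 130/80 meets both goals. On labetalol, escalation begins above 130/80, so second-line therapy can be in place well before 165 or 105. Adding a thiazide to amlodipine satisfies both appendices. Section 7.8.2 lets the Medical Monitor clear treatments that are not listed. All of this stands and limits the consequence. It does not reconcile the texts: a general clause on unlisted treatments does not cancel an explicit restriction, and a drug line should not state a goal that the protocol counts as failure. It is also possible that the Appendix 7 restriction was meant to keep sites away from ACE inhibitors and ARBs, but it does not say so.

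Three stronger readings are tempting and are not supported.

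- A reader might infer that subjects at the highest pressures are denied second-line treatment. Appendix 7 limits new additions only, symptomatic subjects are treated by local practice, and the first-line drugs remain available.
- A reader might infer a separate defect because Appendix 7 points to Section 7.9 for dose decreases and that section describes only a hold in symptomatic cases. No route is blocked. Dose adjustment is in Section 9.1.3.1 and the Appendix 1 note, Section 7.2.2.1 lets the investigator hold doses, Section 7.9 sends subjects without further antihypertensive options to the Medical Monitor, and Section 9.2.5 requests a visit at 165 or 105 whether or not there are symptoms.
- A reader might infer an effect on the efficacy result. Blood pressure is not part of the primary endpoint, and the primary analysis uses all randomized subjects.

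**Conclusion.** Wrong as written, and minor: a safety-consistency point. The amlodipine goal is 10 mmHg looser on each component than the limit used in three body sections, on one of four drug lines. Above 165 or 105, Appendix 7 does not allow two of the four Appendix 1 classes to be newly added, including the only named second-line drug, and it conflicts with Section 7.9 for symptomatic subjects. The practical gap is mainly starting labetalol in an asymptomatic subject with two successive readings above 165 or 105, and even there the Medical Monitor can be asked (Sections 7.8.2, 7.9 and 9.1.3.1).

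The conclusion rests on reading the restriction in Appendix 7 literally and on Section 7.9 being the intended target. The second is well supported by Sections 9.1.3.1 and 9.2.5. The documents do not show which appendix the sponsor meant to prevail on labetalol. They also do not allow the number of affected subjects to be estimated. There is no effect on the sample size, the type 1 error or the primary analysis.

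**What to change.** 1. In the Appendix 1 amlodipine line, replace the goal of below 140/90 with the Section 7.9 target of at most 130/80 mmHg.
2. Amend the Appendix 7 bullet on uncontrolled hypertension so that Appendix 1 second-line therapy (labetalol) may also be added above 165 systolic or 105 diastolic. Keep the ban on starting or changing ACE inhibitors and ARBs. If the sponsor had a reason to exclude labetalol at these pressures, state it and carry the same limit into Appendix 1 and Section 9.1.3.1 instead.

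The cost is a protocol wording amendment and a notice to sites. No visits, staff or procedures are added, and the SAP needs no change.
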